Obstructive Sleep Apnea Treatment to Improve Cardiac Rehabilitation

NCT02005445

Protocol Final Version Date: January 1, 2017

STUDY PROTOCOL

Obstructive Sleep Apnea Treatment to Improve Cardiac Rehabilitation

Overview

The proposed study is a randomized, parallel group study comparing three months of therapy with continuous positive airway pressure (CPAP) to an educational control for patients with comorbid obstructive sleep apnea and coronary heart disease undergoing a structured cardiac rehabilitation program. The study will be conducted over 2 years and participants will be recruited from among patients seen at the VA Boston Healthcare Systems with a diagnosis of coronary heart disease and referred to the Cardiac Rehabilitation Program. A total of approximately 150 patients will be recruited in order to randomize 25 patients to each group (CPAP or Control). Participation of an individual subject will be approximately 1 week for subjects not meeting criteria for randomization, and 8-10 weeks for subjects randomized. Participants will be age 18 and over, of either gender, have a diagnosis of coronary heart disease, and be referred to the Cardiac Rehabilitation Program at the VA Boston Healthcare System. No children or other special classes of individuals will be enrolled. All enrolled subjects will be veterans.

(1) RATIONALE

(a) Statement of the Problem:

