Baseline data will be summarized using standard descriptive statistics for demographic and baseline clinical characteristics by treatment group. Based on our experience with the HeartBEAT Study, the rate of dropouts during the course of the three-month trial is expected to be low and we do not expect dropouts to be differential with respect to treatment group assignment. The main analysis will include all subjects completing the follow-up examination. For the purposes of a sensitivity analysis, a result of “no change” will be imputed for all dropouts, and compared to the main analysis.

The analysis for the primary outcome measure will consist of a one-factor analysis of variance comparing the mean changes from baseline in six minute walk distance. The primary analysis is a simple analysis of variance, with data transformation or adoption of rank-based inference if approximate normality is not present. A p value <0.05 will be considered statistically significant. While the randomization should achieve approximate balance on potentially confounding conditions, analysis of covariance models that employ adjustments for age, sex, sleep apnea severity, comorbid illness, smoking and alcohol use will be fit to potentially improve the efficiency of the treatment effect estimates. Should a significant difference between treatment and comparator be identified, further exploratory analyses will assess the relation of adherence to CPAP therapy to change in outcome measures.

Each of the secondary outcome measures is continuous; therefore, analysis of these variables will be treated in a similar fashion to the analysis of the primary study endpoints.

Sample size and power

Our primary goal is to determine the impact of identification and treatment of obstructive sleep apnea in patients with coronary heart disease undergoing cardiac rehabilitation. Patients will be allocated into the two groups, HLSE or HLSE plus CPAP, randomly according to a 1:1 ratio.

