There are no published data on the effect of CPAP therapy on 6-minute walk distance in patients with coronary heart disease; however, in a recent report from a general sample of patients with OSA, treatment with CPAP was associated with a mean 114 m improvement in 6-minute walk distance after 4 weeks, compared to a control group not treated with CPAP (22). This is well above the minimal clinically important difference of 23 m in 6-minute walk distance reported for patients with stable coronary heart disease (23). The standard deviation in 6-minute walk distance in patients with stable coronary

heart disease has been estimated at 104 m (24), similar to the 90 m estimated for healthy adults (25). Assuming a modest correlation of 0.4 between repeated measures of the 6-minute walk test, the sample size of 25 subjects in each group will have 80% power to detect a difference between groups of 57 m in 6-minute walk distance, half of the difference reported for the effect of OSA treatment (22).

Human Subjects

Potential Risks

The study procedures do not place the subjects at risk of harm or discomfort greater than those encountered in routine medical care. Portable sleep monitoring may lead to minor sleep disturbance and some subjects may experience mild skin irritation from the sensors or electrodes used. The administration of questionnaires may be stressful, although none ask sensitive information.

The study treatment is generally considered quite safe. CPAP is a FDA-approved therapy for the treatment of sleep apnea. The use can be associated with a number of minor side effects, including nasal congestion, runny nose, dry nose or mouth, skin irritation from the mask or headgear, aerophagia or discomfort from the mask or air pressure. Rarely, sinus problems may get worse while using CPAP and mild nose bleeds may occur. These side effects will be minimized by using a humidifier built into the device and by using the most appropriate pressure.

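### The stated 80% power to detect 57 m with 25 per group does not follow from the plan's own inputs, which give about 41% power at 57 m and a detectable difference of about 92 m

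*Combined protocol and SAP*

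**What the plan says.** The Sample size and power section builds the claim in four steps.

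- **Effect.** A report in general OSA patients found a 114 m gain in six-minute walk distance with CPAP. The plan takes half of this, 57 m, as the difference to detect.
- **SD.** The SD in patients with stable coronary "heart disease has been estimated at 104 m (24), similar to the 90 m estimated for healthy adults".
- **Correlation.** "Assuming a modest correlation of 0.4 between repeated measures of the 6-minute walk test".
- **Result.** "the sample size of 25 subjects in each group will have 80% power to detect a difference between groups of 57 m".

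The section gives no formula, no SD of change and no sidedness.

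The Statistical analysis section defines the test. The primary analysis "will consist of a one-factor analysis of variance comparing the mean changes from baseline in six minute walk distance", and "A p value <0.05 will be considered statistically significant". Further models are planned to gain efficiency, namely "analysis of covariance models that employ adjustments for age, sex, sleep apnea severity, comorbid illness, smoking and alcohol use". Baseline walk distance is not among those covariates.

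On numbers, the Overview says that "approximately 150 patients will be recruited in order to randomize 25 patients to each group", while the Statistical analysis section says "The main analysis will include all subjects completing the follow-up examination". Dropout is expected to be low, but no rate is given.

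**The concern.** A correlation below 0.5 makes a change score more variable than a single measurement. With a correlation of 0.4, the SD of change must therefore exceed 104 m. A difference of 57 m is then only about half an SD of change, and 25 per group is well short of what 80% power requires for an effect of that size.

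This sentence is the only statistical justification for the sample size, and it concerns the primary outcome. A reader of a null result who trusts it would think a true 57 m effect had a 20% chance of being missed. On the plan's own inputs that chance is about 59%.

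**Working it through.** **Inputs, all from the plan:** SD 104 m (alternative 90 m, healthy adults); correlation ρ = 0.4; n = 25 per group; difference 57 m; α = 0.05; ANOVA on change with two groups, which is equivalent to a two-sided two-sample t-test with 48 df. **Assumptions added:** equal SD at both visits and in both groups, and no dropout (this favours the stated figure).

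**1. Attempt to reproduce the stated 80% at 57 m**

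- SD of change = SD × √(2(1 − ρ)) = 104 × √1.2 = 113.9 m
- SE of the difference = 113.9 × √(2/25) = 32.2 m
- Noncentrality = 57 / 32.2 = 1.77
- Power from the noncentral t, 48 df = **41%** (normal approximation 42%; simulation of 50,000 trials 41.7%)

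The stated 80% is not reproduced.

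**2. Detectable difference at 80% power**

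The noncentral t gives **92.1 m**. The normal approximation is (1.96 + 0.84) × 32.2 = 90.3 m.

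**3. Other readings, 25 per group, ρ = 0.4.** Each cell gives power at 57 m and the difference detectable with 80% power.

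| Analysis | SD 104, two-sided | SD 104, one-sided | SD 90, two-sided | SD 90, one-sided |
|---|---|---|---|---|
| Change score (as planned) | 41%; 92 m | 54%; 81 m | 52%; 80 m | 64%; 70 m |
| Follow-up value only | 48%; 84 m | 61%; 74 m | 59%; 73 m | 71%; 64 m |
| ANCOVA on baseline walk distance, residual SD = SD × √(1 − ρ²) | 54%; 77 m | 67%; 68 m | 67%; 67 m | 78%; 59 m |

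No cell reaches 80%. The nearest, in the bottom right, departs from the plan on the analysis, the patient SD and the sidedness.

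**4. What the stated result would require**

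Two-sided 80% power at 57 m needs an SD of change of 70.5 m. Solving for the correlation:

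- SD 104 m: ρ = 1 − 70.48² / (2 × 104²) = 0.77
- SD 90 m: ρ = 1 − 70.48² / (2 × 90²) = 0.69

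Two-sided power at 57 m with SD 104 m, by assumed correlation:

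| ρ | 0.4 | 0.5 | 0.6 | 0.7 | 0.77 |
|---|---|---|---|---|---|
| Power | 41% | 48% | 56% | 69% | 80% |

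**5. A possible source of the figure**

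If the factor 2 is left out of the change-score variance, the result comes close to the plan's:

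- 104 × √0.6 = 80.6 m, one-sided: 79% power, 57.5 m detectable
- 90 × √0.6 = 69.7 m, two-sided: 81% power, 56.4 m detectable

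Neither is a valid SD of change. Because the plan shows no calculation, this is a conjecture only.

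**6. Consequences on the plan's inputs**

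- Completers needed for 80% power at 57 m: 2 × (1.96 + 0.84)² × 113.9² / 57² ≈ 63 per group (64 with the t distribution), against 25 randomized.
- Smallest observed difference with two-sided p<0.05: 2.011 × 32.2 = 64.8 m. An observed 57 m gives t = 1.77 and p = 0.083.
- Losing one, two or three completers per group gives 40%, 38% or 37% power at 57 m.

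**The case against.** - **The correlation of 0.4 may be cautious.** The true value could well be higher, and so could the power. But the plan attaches its 80% to 0.4. If a higher value was meant, it has to be stated.
- **Sidedness is not given, and a second SD is quoted.** The shortfall is close to twofold only for SD 104 m and a two-sided test. Otherwise the ratio of stated to derived power is about 1.5 (80/54 or 80/52), or about 1.25 (80/64) with both concessions. This stands as a limit on the size of the error. However, a two-group ANOVA F-test is two-sided in effect and 104 m is the patient figure, so 41% is the right headline.
- **57 m is already half the only treatment effect the plan cites.** At the full 114 m, the same inputs give about 93% power. This is true and worth stating in the plan, but it does not support 80% at 57 m.
- **N also rests on feasibility.** The Sample Selection section gives a recruitment basis (75 screened and 25 randomized per year). The power sentence is therefore the only statistical justification, not the only one.
- **The error leaves type I error, the estimate and its confidence interval untouched.** This is correct. The harm lies in how the design's sensitivity is read.
- **The 65 m threshold and p = 0.083 use the planning SD.** The actual test will use the observed SD, so these two figures are illustrations.
- **Dropout is a side issue.** By the figures above it costs a few points of power at most for small losses, and the plan includes a no-change sensitivity analysis.

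**Conclusion.** The power statement is wrong as written. With SD 104 m, correlation 0.4, 25 completers per group and a two-sided test on change, power at 57 m is about 41% rather than 80%, and the difference detectable with 80% power is about 92 m rather than 57 m. This assumes equal SDs across visits and groups and no dropout. No valid two-group analysis tried with either quoted SD, either sidedness and the stated correlation reaches 80%. The conclusion concerns the consistency of the plan's inputs with its result. It does not claim that 0.4 or 104 m will prove correct in the trial. The sentence must be corrected because it is the sole statistical basis for the sample size.

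**What to change.** 1. Show the formula, the SD of change and the sidedness behind the power statement.
2. If the stated inputs stand, replace the sentence with wording such as: *With an SD of 104 m, a correlation of 0.4 and a two-sided 0.05 test on change scores, 25 completers per group give 80% power to detect about 92 m, about 41% power to detect 57 m and about 93% power to detect 114 m.* Add that dropout lowers these figures, because completers are analysed and the number randomized is not inflated.
3. If a higher correlation was intended, state it with its source. About 0.77 is needed with SD 104 m.
4. Quote baseline-adjusted figures (about 77 m detectable, about 54% power at 57 m) only if the Statistical analysis section is also changed to adjust the primary analysis for baseline walk distance.

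Items 1 to 3 change one paragraph and leave enrolment as it is. The cost is a less favourable stated power. Item 4 costs more, because it changes the primary analysis.
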